-  Seribantumab PK: all patients; in relation to seribantumab infusion
  - a C1W1: immediately after the end of the Seribantumab infusion (+15 mins)
  - b C1W3, C2W1, C2W3: pre-dose
-  Immunogenicity samples should be collected for all patients prior to dosing.
-  In the event a patient experiences an infusion reaction at any point in the study, an anti-Seribantumab antibody assay will be taken within 24 hours of the event, in addition to the scheduled time-points. For patients who experience a Grade 3 or 4 infusion reaction to Seribantumab, an anti-Seribantumab antibody titer will be taken as close to the onset of the infusion reaction as possible, at the resolution of the event and 28 days (+/- 2 days) following the event.
-  Disease evaluation per RECIST version 1.1.
-  Tumor sample is to be collected for all HRG positive patients that receive HRG results for eligibility based on testing of archived samples. An additional sample is not required for patients who underwent a fresh biopsy for eligibility testing.
-  Fulvestrant PK: all patients: prior to seribantumab injection
-  Serum for biomarkers should be collected pre-infusion on week 1 of each cycle for all patients
-  End of treatment (30-day Follow-up) visit should be completed within 30 days of the last dose of study drug
-  Should patients refuse or drop out of survival follow-up, attempts should be made to obtain any death information available via public records.
-  One reading prior to infusion with seribantumab.
-  AE/SAE collection to be included. S/AE assessment and reporting will proceed as outlined in Sections 9.2 and 9.3
-  All patient hospitalizations and/or hospital visits should be collected, whether or not associated with an adverse event.
-  In addition to the timepoints noted, MUGA or Echocardiogram should be performed post-screening for any study patient who develops symptoms consistent with new onset of congestive heart failure.
-  Unless performed within the last 4 weeks as part of assessments in the previous cycle
-  Sample to be collected prior to any study treatment.

Proprietary and Confidential Page 44 of 65

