# 7.5. Electrocardiogram (ECG)

A 12-lead electrocardiogram (ECG) will include a description of the cardiac rate, rhythm, interval durations, and an overall impression. QTc should be calculated using the Fridericia method (QTcF). ECGs will be performed for all patients at screening to rule out clinically significant abnormalities. For randomized patients, ECGs will be performed on week 1 of each cycle prior to dosing with seribantumab.

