#### Table 5.6.4.1 Vital Signs Normal Range

## 5.6.5 Electrocardiogram

The number and percentage of patients with worst ECG result as order: Abnormal, Clinically Significant, Abnormal, not Clinically Significant, Normal will be summarized at screening. Results will be counted once for each patient and scheduled visit.

Exposure-Response Analysis: The relationship between seribantumab plasma concentration and  $\Delta QTcF$  (changefrom-baseline QTcF) will be quantified using a linear mixed effects model with  $\Delta QTcF$  as the dependent variable, plasma concentration as continuous covariate, and treatment (active or placebo) and time as categorical factors, and a random intercept and slope per subject. The geometric mean of the individual Cmax values for subjects on seribantumab will be determined. The predicted effect and its two-sided 90% CIs for  $\Delta\Delta QTcF$  (placebo-corrected change-from-baseline QTcF) at this geometric mean Cmax will be obtained.

By-Timepoint Analysis: The analysis for QTcF will be based on a linear mixed effects model with ΔQTcF as the dependent variable, baseline QTcF as covariate, and time (categorical), treatment (seribantumab and placebo), and time by treatment interaction as factors. An unstructured covariance matrix will be specified for the repeated measures at post-dose timepoints within subject. If the model with unstructured covariance matrix fails to converge, other covariance matrix such as compound symmetry can be considered. For this analysis a 90% 2-sided confidence interval (CI) will be calculated for the contrasts " seribantumab - placebo" for each time point, separately. For change-from-baseline as well as the placebo-corrected change-from-baseline HR, PR, and QRS, descriptive analysis including number of subjects, mean, median, min, max, standard deviation (SD), standard error (SE), and 90% confidence interval (CI; from t-distribution) will be calculated for each treatment and timepoint.

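### SAP 5.6.5 predicts the QTcF effect at Cmax, but the protocol gives one drug-exposed ECG and concentration pair per patient, at trough, so the prediction is an unverifiable extrapolation

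*SAP*

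**What the plan says.** **SAP 5.6.5, exposure-response analysis.** Change from baseline in QTcF is modelled on plasma concentration (continuous), with treatment and time as categorical factors and "a random intercept and slope per subject". Then: "The geometric mean of the individual Cmax values for subjects on seribantumab will be determined". The placebo-corrected effect and its two-sided 90% CI are to be predicted at that concentration. The same section also plans a by-timepoint mixed model and categorical outlier tables.

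**Protocol, ECG schedule.** Section 7.5: "For randomized patients, ECGs will be performed on week 1 of each cycle prior to dosing with seribantumab". The footnote to the ECG row in Section 6.1 says the same: "One reading prior to infusion with seribantumab". No post-infusion ECG is scheduled.

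**Protocol, PK schedule.** Section 6.1 and Table 4 (Section 8.5.1) give one post-infusion sample, at the end of the Cycle 1 Week 1 infusion. The others are "C1W3, C2W1, C2W3: pre-dose". Sampling stops with Cycle 2.

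**Protocol, planned ECG analysis.** Section 10.5.4 plans only tabulation of change from baseline by time point. Sections 2.1 to 2.3 contain no ECG objective.

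**Origin of the SAP.** SAP Section 1 names protocol 02-03-10, whereas this protocol is 02-02-10. SAP 1.2 describes a phase 3 trial of exemestane or fulvestrant, and SAP 1.3 lists an ECG objective.

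**The concern.** A concentration-QTc model can speak about peak exposure if ECGs and concentrations have been observed together over a range that reaches the peak. Here they have not. The SAP nevertheless commits to a QTcF estimate with a confidence interval at Cmax, where no ECG is taken.

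Two things are at stake. First, the report would carry a peak-exposure QTc figure that depends on an assumption of linearity the trial cannot test. Second, the other planned QTcF analyses use the same pre-infusion ECGs. Unless they are labelled as trough results, a reader could take them as a general QT assessment. An effect confined to the period around peak would be missed by all of them.

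**Working it through.** The documents state no Cmax, trough or QTc precision, so there is no plan figure to reproduce.

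**1. Matching ECGs to concentrations**

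| Visit | ECG | Seribantumab PK | Usable drug-exposed pair |
|---|---|---|---|
| Cycle 1 Week 1 | before infusion | end of infusion | no: the ECG is drug-free |
| Cycle 1 Week 3 | none | pre-dose | no |
| Cycle 2 Week 1 | before infusion | pre-dose | **yes, at trough** |
| Cycle 2 Week 3 | none | pre-dose | no |
| Cycle 3 onward, Week 1 | before infusion | none | no |

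This gives one pair per seribantumab patient. The only sample near Cmax has no post-dose ECG beside it. If the screening ECG is taken as baseline, the Cycle 1 Week 1 ECG adds a point at zero concentration and nothing more.

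**2. Size of the extrapolation**

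Inputs: 3000 mg over 1 hour every 2 weeks (Protocol 5.2.3), and the two-compartment typical values of Table 3 (Section 1.6.3): CL 3.15 L/wk, V 3.23 L, Q 2.92 L/wk, V2 2.68 L.

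- Rate constants per week: k10 = 3.15/3.23 = 0.975; k12 = 2.92/3.23 = 0.904; k21 = 2.92/2.68 = 1.090.
- α + β = k10 + k12 + k21 = 2.969 and αβ = k10 × k21 = 1.063, so α = 2.553 and β = 0.416.
- Weights: A = (α − k21)/(α − β) = 0.685; B = (k21 − β)/(α − β) = 0.315.
- D/V = 3000/3.23 = 929 mg/L. Elimination during the 1-hour infusion brings the first-dose peak to 924 mg/L.
- Contribution of one dose after t weeks: 929 × (A·e^(−αt) + B·e^(−βt)). This gives 131 mg/L at 2 weeks and 55 mg/L at 4 weeks.
- Cycle 2 Week 1 trough = 131 + 55, or 187 mg/L before rounding.

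Ratios to that trough: first-dose peak 924/187 = 4.9; peak after the Cycle 2 Week 1 dose 1110/187 = 5.9; steady-state peak 1153/187 = 6.2. The first is the relevant one, because only the first-dose peak is sampled.

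Sensitivity of the first-dose ratio:
- CL one omega (36%) lower or higher, that is × 0.70 or × 1.43: 3.2 or 8.7.
- Sex effect on CL (0.255, coding and reference sex not given) lowering or raising CL: 3.4 to 3.6, or 7.0 to 7.3.
- Simulation of 4000 patients with the Table 3 random effects, trying several readings of the CL-V covariance: ratio of geometric means 5.0 to 5.2. No simulated trough reached the geometric mean Cmax. The highest of 40 troughs was typically about 415 to 430 mg/L.

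**3. Precision at Cmax**

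Placebo concentrations are zero and treatment is a separate factor in the model. The slope is therefore learned from the spread of troughs among seribantumab patients:

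SE at Cmax = s × √[2/n + (Cmax − trough)² / ((n − 1) × SD²)]

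Here n = 40 per arm (80 randomized 1:1), trough SD is 90 mg/L (assumed, from the simulation) and s is the residual SD of QTcF change (assumed 10 to 20 ms).

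- s = 10: 1.645 × 10 × √[2/40 + 737²/(39 × 90²)] = 16.45 × √(0.050 + 1.719) = 21.9 ms.
- s = 20: 43.8 ms.
- At the trough itself, 1.645 × s × √(2/40) = 3.7 to 7.4 ms.
- With trough SD between 75 and 110 mg/L, the half-width at Cmax runs from 18 ms (s = 10, SD 110) to 52 ms (s = 20, SD 75). With 32 per arm and SD 90 it is 24.5 to 49.1 ms.

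**4. What a trough ECG would show**

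If the effect is linear in concentration, 10 ms at Cmax appears as 10 × 187/924 = 2.0 ms at the Cycle 2 Week 1 trough.

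**The case against.** The strongest case for leaving the SAP alone has four parts.

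- **The output would expose its own weakness.** A reader might infer that the prediction could give false reassurance through a narrow interval at Cmax. The calculation does not support that. On the formula above, a half-width below 10 ms needs a residual SD of about 4.6 ms or less (10 ÷ (1.645 × 1.330)). An imprecise interval is the likelier outcome. This changes the nature of the harm but does not make the estimate worth reporting.
- **The model is not wholly inestimable.** This is correct. Repeated ECGs per patient support a random intercept, and the population slope can be estimated from differences in trough between patients. What lacks support is the per-subject random slope: with one drug-exposed pair it cannot be separated from residual error within a patient.
- **Population PK could supply concentrations at later ECGs.** Protocol 10.5.6 plans population PK, although SAP 5.6.8 specifies non-compartmental analysis. Predicted values would add pairs, but all of them at trough, so the extrapolation would remain.
- **This is a symptom of a larger mismatch.** The SAP names another protocol and an ECG objective this trial lacks, so the model appears to be carried over. That probably explains the problem and should be handled with the wider reconciliation. The passage still needs a specific correction.

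A reader might also think a peak estimate is available at no cost by pairing the existing Cycle 1 Week 1 ECG with the end-of-infusion sample. It is not: that ECG is taken before any drug, so a drug-free QTcF would be labelled as peak exposure.

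**Conclusion.** The point holds as a mismatch between an SAP analysis and the data the protocol will collect. The per-subject random slope is not identifiable from the scheduled pairs. The prediction at Cmax lies about 5-fold above the exposure at which QTcF is observed, with a plausible range of about 3 to 9, and linearity over that gap cannot be checked.

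The likely product is an assumption-driven estimate with a 90% CI half-width of about 22 to 44 ms. The clearer risk of misreading lies in the by-timepoint and outlier analyses, which will look precise but describe trough only.

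The schedule finding rests on the documents alone. The fold figures are derived from Table 3 and depend on clearance and on a sex effect whose coding is not given. The precision figures also rest on the assumed residual and trough SDs. The documents give no basis for saying that a QT effect exists, and the primary endpoint is untouched. The change should be made because it is cheap and the present text promises something the data cannot deliver.

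**What to change.** In SAP 5.6.5:

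1. Delete the exposure-response paragraph's random-slope model and the prediction of placebo-corrected QTcF change at geometric mean Cmax.
2. Keep the by-timepoint QTcF model and the categorical outlier tables.
3. Add a sentence such as: all on-treatment ECGs are pre-infusion, so the QTcF results describe trough exposure only and support no conclusion about QTc at peak concentration.

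This brings the SAP closer to Protocol 10.5.4. It needs no protocol amendment and no new data. The cost is that the trial makes no QTc statement at peak exposure, which the present schedule could not support in any case.

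If the sponsor wants a peak estimate, an ECG would have to be moved to, or added at, a time after infusion alongside a PK sample. That is a protocol change and not part of this correction.

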## 5.6.8 Pharmacokinetic (PK)

A Non-compartmental Analysis (NCA) will be used to analyze the pharmacokinetic parameters based on plasma concentration versus time. Mean concentration curves will be displayed using linear and semi-log scales. Standard errors will be displayed on the graphs for each collection day. A summary of PK parameters will be developed for each study drug and will include the previously indicated parameters. Additional analyses may be performed if deemed necessary.

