# 8.5. Pharmacokinetic Testing

## 8.5.1. Seribantumab PK Samples

Blood samples will be collected from all patients to determine the levels of monoclonal antibodies that comprise seribantumab. The serum PK analysis will be performed post-dose on Cycle 1, Week 1, and pre-dose for all subsequent seribantumab infusions until the completion of Cycle 2, as outlined in Table 4. Approximately 5 mL of blood will be collected. The real time of blood collection must be documented in the respective eCRF. A laboratory manual will be provided with instructions for collecting, processing, and shipping the samples.

PK samples should be collected at the following time-points relative to the seribantumab infusion:

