#### 8.5.2. Fulvestrant PK samples

To determine the levels of fulvestrant, blood samples will be collected for all patients prior to the seribantumab dose on Cycle 1, Week 1, Cycle 1, Week 3, Cycle 2, Week 1, and Cycle 2, Week 3

Approximately 5 mL of blood will be collected. The real time of blood collection must be documented in the respective eCRF. A laboratory manual will be provided with instructions for collecting, processing, and shipping the samples.

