### 10.5.6. Pharmacokinetic Analyses

Serum concentrations will be used to determine PK parameters for seribantumab and fulvestrant as appropriate using population pharmacokinetic analysis. The resulting PK parameters will be associated with efficacy and safety endpoints as appropriate. Details will be provided in a separate population PK analysis plan.

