# **ABBREVIATIONS**

AE	Adverse event
AUC	Area under the curve
BSA	Body Surface Area
CBR	Clinical benefit rate
CI	Confidence Interval
Cmax	Maximum serum concentration
CR	Complete Response
CRF	Case report form
CSR	Clinical study report
CT	Computed tomography
CTCAE	Common terminology criteria for adverse events
DMC	Data Monitoring Committee
DOR	Duration of Response
DSMB	Data Safety Monitoring Board
ECG	Electrocardiogram
ECHO	Echocardiogram
eCRF	Electronic case report forms
EDC	Electronic data capture
FDA	Food and Drug Administration
HRG	Heregulin
ICH	International conference on harmonization
ITT	Intent-to-Treat
IWRS	Interactive web response system
LVEF	Left ventricular ejection fraction
MedDRA	Medical Dictionary for Regulatory Activities
Mth	Month
MUGA	Multiple gated accession scan
NCI	National Cancer Institute
NE	Not Evaluable
ORR	Objective response rate
OS	Overall Survival
PD	Progressive disease
PFS	Progression free survival
РК	Pharmacokinetic
PR	Partial response
РТ	Preferred term
QTcF	Fridericia's QT correction
RECIST	Response Evaluation Criteria In Solid Tumors
SAE	Serious adverse event

Version Date: 29Jan2016

SAP	Statistical Analysis Plan
SD	Stable Disease
SOC	System Organ Class
SRB	Safety Review Board
Tmax	Time to maximum serum concentration
t 1/2	Terminal elimination half-life
TFL	Tables, Figures, Listings
TTF	Time to treatment failure
ULN	Upper limit of normal
Vdss	Volume of distribution at steady state
Wk	Week

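### SAP 5.6.8 prescribes non-compartmental PK where the protocol prescribes population PK, and the protocol's sparse samples cannot support it

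*SAP*

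**What the plan says.** **Method.** SAP 5.6.8 states: "A Non-compartmental Analysis (NCA) will be used to analyze the pharmacokinetic parameters based on plasma concentration versus time". It asks for a parameter summary for each study drug and says that this summary "will include the previously indicated parameters". No section of the SAP body sets out such a list. The only PK parameter named in the body is Cmax, in the ECG exposure-response model of 5.6.5. AUC, Tmax, Vdss and "Terminal elimination half-life" occur only in the abbreviation list.

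Protocol 10.5.6 derives the parameters of seribantumab and fulvestrant "as appropriate using population pharmacokinetic analysis", and adds: "Details will be provided in a separate population PK analysis plan".

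**Seribantumab samples.** Protocol 8.5.1 places them "post-dose on Cycle 1, Week 1, and pre-dose for all subsequent seribantumab infusions until the completion of Cycle 2". Table 4 and footnote 7 of the schedule in 6.1 give one sample at the end of the first infusion (within 15 minutes after it) and pre-dose samples at Cycle 1 Week 3, Cycle 2 Week 1 and Cycle 2 Week 3.

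**Fulvestrant samples.** Under protocol 8.5.2, "blood samples will be collected for all patients prior to the seribantumab dose" at Weeks 1 and 3 of Cycles 1 and 2.

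**Status.** The PK profile of both drugs is a secondary objective (protocol 2.2). SAP 5.2 commits every analysis in the SAP to the final study report.

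**The concern.** Two governing documents give different methods for the same secondary objective. Protocol section 10 allows the SAP to modify the protocol's plans, but SAP 1.1 declares no change to the PK analysis, so this reads as a conflict and not as a decision.

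The method that the SAP names is also the one that the samples cannot support. NCA builds AUC from the observed points and takes half-life from a log-linear terminal segment. Protocol 1.6.3 describes seribantumab with a two-compartment model, and no sample falls between the end of the first infusion and day 14. A line drawn between those two points cannot show the distribution phase.

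At stake are PK tables in the study report that could be biased or empty, and that could disagree with the population PK results for the same patients.

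**Working it through.** **1. Inputs.** Protocol Table 3: CL 3.15 L/wk, V 3.23 L, Q 2.92 L/wk, V2 2.68 L. Protocol 5.2.3: 3000 mg over 1 hour on days 1 and 15 of 28 (interval 2 weeks).

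**2. The plan's own figure.** Protocol 1.6.3 says that 3 g every 2 weeks has a steady-state average concentration comparable to 20 mg/kg weekly after a 40 mg/kg load. Average concentration = dose / (CL × interval).
- 3 g every 2 weeks: 3000 / (3.15 × 2) = 476 mg/L.
- 20 mg/kg weekly at 75 kg (the weight implied by pairing 20 mg/kg with 1.5 g): 1500 / 3.15 = 476 mg/L.

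The claim reproduces, so Table 3 is a fair basis for the next steps. The protocol states no AUC or half-life to check.

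**3. Model profile for seribantumab.**
- k10 = 3.15/3.23 = 0.975, k12 = 2.92/3.23 = 0.904, k21 = 2.92/2.68 = 1.090 per week; their sum is 2.969.
- α, β = [2.969 ± √(2.969² − 4 × 0.975 × 1.090)] / 2 = 2.553 and 0.416 per week.
- Half-lives, 7 × ln 2 / rate: distribution 1.9 days, terminal 11.7 days.
- Concentrations at the sampling times: 924 mg/L at the end of infusion; troughs 131, 187 and 211 mg/L on days 14, 28 and 42.
- Model AUC over 14 days: 645 mg·wk/L (4512 mg·d/L). AUC to infinity: 3000/3.15 = 952 mg·wk/L.

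**4. NCA on the same samples.** The first interval has two points. Later intervals have troughs only, and these rise with accumulation, so they give no terminal slope. With the end of infusion at 1/168 = 0.006 week:
- Two-point slope: ln(924/131) / (2 − 0.006) = 0.978 per week.
- Area during the infusion (triangle): about 3 mg·wk/L.

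| Quantity (seribantumab) | Two-point NCA | Model | Error |
|---|---|---|---|
| AUC 0–14 d, linear | (924 + 131)/2 × 1.994 + 3 = 1055 | 645 | +64% |
| AUC 0–14 d, log | (924 − 131)/0.978 + 3 = 813 | 645 | +26% |
| Half-life | 7 × 0.693/0.978 = 5.0 d | 11.7 d | −57% |
| AUC to infinity, log | 813 + 131/0.978 = 947 | 952 | −1% |

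Leaving out the triangle, or sampling at the end of the 15-minute window, moves the AUC errors only to about +63% and +25%.

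**5. Spread between patients.** 2000 patients were simulated for each CL–V correlation tried, from 0 to 0.55. Table 3's 36% (CL) and 37% (V) were taken as log-scale standard deviations, without residual error. The widest 5th–95th percentile errors were +22% to +190% (linear AUC), +11% to +67% (log AUC), −67% to −47% (half-life) and −25% to +45% (log AUC to infinity).

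**6. Fulvestrant.** Samples precede the seribantumab dose, and the sections cited do not fix the order of injection and infusion. Fulvestrant is given on days 1 and 15 of Cycle 1 and then only on day 1 of each cycle (protocol 5.3.2). The Cycle 2 Week 3 sample therefore falls about 14 days after an injection, in mid-interval. No peak sample is scheduled, and four such points cannot trace a profile for NCA. The documents give no fulvestrant model, so no bias is computed.

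**The case against.** The strongest reply has four parts.

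- **The objective already has a suitable method.** Protocol 10.5.6 provides population PK for both drugs in its own plan. This stands. A reader might infer that the PK objective fails; the documents do not support that. What remains is that SAP 5.2 would still send the NCA output to the study report.
- **SAP 5.6.8 names neither AUC nor half-life.** This stands. A reader might infer that the SAP plans to report them with bias, but that rests on the abbreviation list. The list also carries CBR, DOR and TTF, for which the SAP specifies no analysis, so it is weak evidence. The missing parameter list is a defect in its own right.
- **The size depends on choices the SAP does not make.** It sets no trapezoid rule, AUC interval or slope rule, and SAP 4.4 sets non-computable values to missing. A rule that needs three points for the slope would leave half-life blank instead of wrong. AUC to infinity by the log method is close for the typical patient. All of this stands, although a blank result does not characterise the profile either, and individual errors in AUC to infinity remain wide.
- **Fulvestrant is not sampled only before its own dose.** A reader might infer this from the timing rule, but the Cycle 2 Week 3 sample contradicts it. The sampling is sparse and has no scheduled peak, which is enough for the point.

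**Conclusion.** The conflict between SAP 5.6.8 and protocol 10.5.6 is plain on the text, and the scheduled samples do not support NCA for either drug. The size is conditional. If the unlisted parameters include AUC and half-life, two-point NCA overstates typical seribantumab AUC over 14 days by about 25% to 63%, and it gives a half-life of 5.0 days against 11.7 or none at all. This assumes Table 3 typical values, no covariate effects, no residual error and sampling at nominal times.

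The likely root cause is that the SAP was written for another trial. Its section 1 names protocol seribantumab-02-03-10, whereas this protocol is MM-121-02-02-10, and its section 1.2 describes a phase 3 study with exemestane or fulvestrant.

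The point should be corrected before the SAP is used. It does not touch the primary analysis or the sample size.

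**What to change.** - In SAP 5.6.8, replace the NCA sentence with a reference to the population PK analysis and plan of protocol 10.5.6. Leave the model structure for each drug to that plan: the documents support a two-compartment model for seribantumab only, not for intramuscular fulvestrant.
- Limit the SAP's PK tables to observed concentrations at the scheduled times: end of infusion and troughs for seribantumab, and the four scheduled samples for fulvestrant, labelled by time since the last fulvestrant injection.
- Replace the reference to unlisted parameters with an explicit list that contains no NCA-derived AUC, half-life, Tmax or Vdss. State which concentration serves as Cmax in SAP 5.6.5.
- Make the change as part of aligning the whole SAP with this protocol, since rewording 5.6.8 alone leaves the root cause in place.

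For this point the cost is SAP wording. It needs no new samples, and the protocol already promises the population PK plan.
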